7 INVESTIGATIONAL PLAN

7.1 STUDY DESIGN AND PLAN

This is a Phase 2 prospective, multicentre, randomized, double-blind, placebo-controlled study includes a total 36 patients with a diagnosis of Primary Biliary Cholangitis. The study will be conducted over a period of up to 26 weeks and will include a 6-week Screening Phase, a 16-week Treatment Phase and a safety follow-up visit after 4 weeks.

Screening Phase:

- Visit 1 (Day -42): Patient eligibility for participation in the study will be assessed. Medical history will be obtained and physical examination, electrocardiogram (ECG) and laboratory evaluations (including serology, [anti-nuclear antibody, smooth muscle antibody and serum immunoglobulin level G], clinical chemistry, hematology, liver biochemistries, and urinalysis) will be performed. In patients with ANA or SMA antibody positive titers, a liver biopsy must have been performed to rule out autoimmune hepatitis or overlap syndrome. Female patients will undergo a pregnancy test. Serum ALP must be ≥ 1.67 upper limit of normal (ULN) to proceed further in the study.
- Visit 2 (Day -14 to -7): Liver biochemistries (ALT, ALP, total bilirubin (TB) and INR will be re-measured approximately 4 weeks from Day -42 to determine eligibility. Elevated ALP must be ≥ 1.67 ULN on 2 occasions in the Screening Phase and is necessary for study entry. If there is an increase of more than 30% in the levels of ALT, total bilirubin or INR at Day (-14) to Day (-7) [Visit 2] as compared to the values on Day (-42) [Visit 1], then such patients will not be eligible for study entry. The average of two assessments (Visit 1 and Visit 2) of liver biochemistries and INR will be considered as baseline values for these parameters.

Randomization & Treatment Phase:

- Visit 3: The Randomization & Treatment Phase will include 6 outpatient visits over a period of 16 weeks, including the randomization visit. Patients will be randomly assigned to receive either Saroglitzaz magnesium (2 mg or 4 mg) or placebo orally

once daily in addition to their ongoing treatment with UDCA (Patients unable to tolerate UDCA will receive only the investigational medicinal products), starting on Day 1 and continuing for 16 weeks. Efficacy and safety parameters will be assessed during each study visit as per the Schedule Visit Table 1.

- Visit 3.1: Patient will visit study site at 2 weeks after randomization visit for LFTs. The LFTs will be performed at local laboratory.
- Visits 4, 5 and 6: Patients will visit the study site at Week 4 (Visit 4), Week 8 (Visit 5) and Week 12 (Visit 6) for clinical assessment, dispensation and/or reconciliation of study drug, and measurements of efficacy endpoints.
- End-of-Treatment Visit (Visit 7): An End-of-double-blind treatment will occur at Week 16. The clinical assessment, reconciliation of study drug, and measurements of efficacy and safety endpoints will be performed as per the schedule.

Safety follow-up visit (Visit 8) will occur 4 weeks (\pm 3 days) after the End-of-treatment Visit for safety monitoring. Clinical examination and safety lab assessment will be performed during this visit.

7.2 STUDY PROCEDURES AT EACH VISIT

Study schedule for the trial is given in Table 1.

- **Screening Visit (Week -6)**

All subjects will be required to sign the informed consent forms (ICF) after understanding the ICF before any trial related procedure is initiated as per the applicable regulatory guideline.

Informed consent process will be documented in source document, ICF and other relevant logs, and signed with dated by the Investigator or designee. Prior to subject participation in the trial, written informed consent will be obtained from each subject (or the subject's legally accepted representative) according to the regulatory and legal requirements of the participating state and country.

Subjects with the history of PBC will be screened for eligibility to participate in the study. Demographic detail, medical history will be recorded. ECG will be performed. Pregnancy test will be performed for women of childbearing potential.

Vital signs, height and weight measurements, and physical and laboratory examinations listed in Table 1 will be carried out in subjects suffering from PBC; those satisfying the inclusion-exclusion criteria will be invited to participate in this study. (The physical examination will consist of an evaluation of the head, neck, eyes, ears, nose, throat, chest, heart, lungs, abdomen, skin, extremities, and the neurological and musculoskeletal systems). Concomitant medications will be recorded. Serum ALP must be ≥ 1.67 upper limit of normal (ULN) to proceed further in the study.

Visit 2 (Week -2 to -1): Liver biochemistries (ALT, ALP, total bilirubin (TB) and INR will be re-measured approximately 4 weeks from Day -42 to determine eligibility. Physical examination, vital signs and lab investigation will be performed as per Table 1.

Elevated ALP must be ≥ 1.67 ULN on 2 occasions in the Screening Phase and is necessary for study entry. If there is an increase of more than 30% in the levels of ALT, Total bilirubin or INR at Day(-14) to Day(-7)[Visit 2] as compared to the values on Day (-42)[Visit 1], then such patients will not be eligible for study entry.

The average of two assessments (Visit 1 and Visit 2) of liver biochemistries and INR will be considered as baseline values for these parameters.

- **Visit 3: Randomization Visit (Week 0±3 days)**

After screening, the eligible patients will be randomly assigned to one of the following treatment groups in addition to their ongoing treatment with UDCA (Patients unable to tolerate UDCA will receive only the investigational medicinal products) i.e., Saroglitzaz magnesium 2 mg, Saroglitzaz magnesium 4 mg, or placebo. Vital signs measurements, weight measurements, physical examination, and laboratory examination will be performed as mentioned in Table 1. Concomitant medications will be recorded. AEs will be noted, if any. Urine pregnancy test will be performed for women of childbearing potential. Subjects will undergo cardiac evaluation (ECG). A 4-week supply of study medication (one bottle) will be dispensed. Baseline quality of life assessment will be performed.

- **Visit 3.1 (Week 2±3 Days)**

Patient will visit study site at 2 weeks after randomization visit for LFTs. The LFTs will be performed at local laboratory.

- **Visit 4 (Week 4±3 Days), Visit 5 (Week 8±3 Days) and Visit 6 (Week 12±3 Days)**

Subjects will be undergo a physical examination and laboratory parameters (safety and efficacy) will be assessed as per Table 1. Vitals signs, body weight will be recorded.

AEs, if any, will be noted. Urine pregnancy test will be performed for women of childbearing potential. Concomitant medications will be recorded. Medication compliance will be checked. Medication will be dispensed on each visit for next 4 weeks.

- **End-of-treatment Visit 7 (Week 16±3 Days)**

Subjects undergo physical examination and laboratory parameters (safety and efficacy) will be assessed as per Table 1. Vitals signs and weight will be recorded. AEs will be noted, if any. Subjects will undergo cardiac (ECG) evaluation. Pregnancy test will be performed for all women of childbearing potential. Concomitant medications will be recorded. Medication compliance will be checked.

- **Safety follow-up Visit 8 End of Study (Week 20±3 Days)**

A safety follow-up visit will be performed 4 weeks after End-of-treatment Visit. Patients clinical examination and safety lab assessment will be performed as per Table 1.

Unscheduled visits- will be allowed any time during the study for assessment and management of AEs and any concurrent clinical conditions. Unscheduled visits shall be captured in the CRF.

- If further investigations are required in case of any AE, Investigator will assess the AE and take necessary action, if required.

- During this 16-week program, if it is necessary to follow-up on any AE, a designated person from the center will interview the subject for his/her general health, telephonically.

If subject discontinues the study, due to any reason, before End of Treatment Visit, all procedures of End of Treatment Visit should be carried out.

7.3 PHARMACOKINETIC ASSESSMENT

Eighteen subjects will participate in a pharmacokinetic sub-study. Additional patients may be enrolled into the study to ensure the pharmacokinetic assessment is performed on at least 6 completed patients in each treatment arm.

On Study Visit 3, and Study Visit 7 subjects will be asked to remain at the clinic for 10 hours. On these dates, additional blood samples will be collected at the following time-points: pre-dose (0.0), 0.5, 1.0, 2.0, 3.0, 4.0, 6.0, 8.0, and 10.0. Subjects will be asked to return to the clinic the following day for another collection approximately 24 hours after study drug administration on Visit 3 and Visit 7. In addition to these collections, pre dose blood samples will be collected at Study Visits 4, 5, and 6.

The pharmacokinetic blood samples will be sent to a central laboratory as assigned by the sponsor. The total amount of blood drawn for Pharmacokinetic study from each patient over the study will be less than ~120 mL/25tablespoons. A detail pharmacokinetic study plan will be prepared separately.

7.4 ADHERENCE TO PROTOCOL

Investigator shall strictly adhere to the protocol and Good Clinical Practice (GCP) guidelines. All subjects will be strictly required to follow the instructions given to them as per this protocol. For any deviation or violation from protocol, considered serious, the subject may be withdrawn from the trial at the discretion of the Sponsor or the Investigator.

7.5 PROTOCOL DEVIATIONS

For the purposes of this study, no distinction will be made between Protocol Violations and Deviations. Deviations may be categorized as minor protocol deviation and a major protocol deviation. Minor protocol deviation includes any deviations that do not necessarily influence

**Zydus Discovery
DMCC**

CLINICAL TRIAL PROTOCOL

Saroglitazar Magnesium – Phase II

SARO.16.004

CONFIDENTIAL

PAGE 55 OF 82

the results/outcome of primary endpoints or subject safety. Minor protocol deviations do not require immediate notification to the IEC/IRB unless otherwise specified by IEC/IRB requirements. All minor protocol deviations will be noted in monitoring reports and provided to the investigator.

Major protocol deviation includes any violation which may influence the results/outcome of primary endpoints or subject safety. Major protocol deviations must be reported immediately to the IRB/IEC as specified by the IRB/IEC requirements. All Major protocol deviations will be reported to the Sponsor immediately.

Note: persistent non-compliance of minor protocol deviations may rise to the level of major protocol deviations.

The Sponsor reserves the right to terminate the study at a given center in the event of monitoring and/or auditing findings of serious or persistent non-compliance with the protocol, SOPs, GCP, and/or applicable regulatory requirement(s) by an investigator/institution. In all case of site closure due to protocol deviations, the IEC/IRB and regulatory authority will be informed.

The clinical study report will provide the list of protocol deviation/violation on separate section. The result will be analysed for all participants with major protocol deviations.

Protocol deviation/violation will include but are not limited to the following;

- Subjects that did not meet entry criteria
- Subjects that developed withdrawal criteria but were not withdrawn
- Subjects that received the wrong treatment or incorrect dose
- Subjects that received an excluded medication

7.6 DATA MONITORING COMMITTEE

Safety data including adverse events and liver-related events (i.e., clinically meaningful elevations in liver biochemistries ALT, AST, and bilirubin) will be reviewed regularly by a Data Monitoring Committee. The Data Monitoring Committee will have a formal structure and will operate according to a previously agreed upon remit.

Approved by:
[name]

Protocol No. SARO.16.004
Version No.: 6.0

8 BIOSTATISTICS

8.1 STATISTICAL DESIGN

Statistical Analysis Plan (SAP) will be prepared and finalized prior to database lock. The SAP will include detailed statistical aspects of the safety and efficacy analysis. Statistical analysis will be performed using SAS® (version 9.4 or higher) software (SAS Institute Inc., USA).

8.2 NULL AND ALTERNATIVE HYPOTHESIS

Below is the hypothesis of primary efficacy endpoint:

Null hypothesis: $H_0: \mu_s = 0$

Alternative hypothesis $H_1: \mu_s > 0$

Where: μ_s = change from baseline in ALP levels of the Saroglitazar magnesium (2 mg and 4 mg).

Rejection of the null hypothesis will lead to conclude that the change from baseline in Saroglitazar magnesium 2 mg and 4 mg is statistically significant and hence the test drug is effective.

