6 OBSERVATIONS

6.1 EFFICACY

6.1.1 Primary Endpoint

1. Improvement in ALP levels after 16 weeks of Saroglitazar magnesium 2 mg and 4 mg treatment.

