8.3.2.1 Primary Efficacy Analysis

The primary analysis for the primary efficacy endpoint will be based on the MITT. The primary efficacy endpoint in this study is improvement in ALP levels after 16 weeks in Saroglitazar magnesium treatment.

The primary endpoint will be summarized and improvement from baseline to week 16 will be evaluated using Paired t-Test. Statistical significance will be defined as a p-value <0.05.

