8.3.2.2 Secondary Efficacy Analysis

Each secondary efficacy endpoint will be summarized by treatment group at each time point, as appropriate.

Following secondary endpoints will be analyzed:

- Change from baseline in ALP at Week 4, Week 8, Week 12 and Week 16 in Saroglitazar magnesium as compared to placebo.

Approved by: [name]	Protocol No. SARO.16.004 Version No.: 6.0
----------------------------------	--

- Change from baseline in lipid profile (TG, TC, HDL, LDL, and VLDL) at Week 4, Week 8, Week 12 and Week 16 in Saroglitzaz magnesium as compared to placebo.
- Change from baseline in liver biochemistries (GGT, ALT, AST, bilirubin and albumin) at Week 4, Week 8, Week 12 and Week 16 in Saroglitzaz magnesium as compared to placebo.
- Change from baseline in serum total bile acids at Week 4, Week 8, Week 12 and Week 16 in Saroglitzaz magnesium as compared to placebo.
- Change from baseline in 7α -hydroxy-4-cholesten-3-one (C4) and fibroblast growth factor 19 (FGF 19) at Week 16 in Saroglitzaz magnesium as compared to placebo.
- Proportion of patients with ALP improvement, i.e. 15%, 20%, 30%, 40% and normalization at Week 8 and Week 16.
- Change in QoL at Week 16 by using PBC40.
 - This instrument consists of 6 domain and 40 questions: symptoms, itch, cognition, emotion and social.
- Change from baseline in ALP in patients who are unable to tolerate UDCA at week 16 in Saroglitzaz 2 mg and 4 mg as compared to Placebo.
- Pharmacokinetics of Saroglitzaz.

The change from baseline will be determined as:

Change = (Post-baseline – Baseline)

Percent Change = (Post-baseline – Baseline) / Baseline * 100

Treatment effects will be estimated using the least-square mean, standard error and 95% confidence intervals from ANCOVA model with baseline value as covariate. Comparison will be done for Saroglitzaz magnesium (2 mg and 4 mg) and placebo using the difference in least-square means from the ANCOVA model. Proportion of patients with ALP

improvement, i.e., 15%, 20%, 30%, 40% and normalization at Week 8 and Week 16 will be presented as counts and percentages.

Descriptive statistics will be provided for each pharmacokinetic parameter.

The following pharmacokinetic parameters will be evaluated:

- i. Peak Plasma concentration (Cmax)
- ii. Time to reach peak Plasma concentration (Tmax)
- iii. Area under Plasma concentration vs. time curve till the last time point (AUC0-t)

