6. EFFICACY ANALYSIS STRATEGY

6.1 General Considerations

Categorical variables will be summarized with the frequency and percentage of patients in each category. Continuous variables will be summarized descriptively with the number of subjects, mean, standard deviation, minimum, median and maximum values. Change from baseline will be summarized similarly, but also with standard error. The change from baseline will be calculated as follows:

Change from baseline = Post baseline value – Baseline value

Percent Change = (Post baseline value – Baseline value) / Baseline value * 100.

Decimal Precision

Unless otherwise noted, means, medians, standard deviations, minimums and maximums will be presented to two decimal places, percentages and confidence intervals will be presented to one decimal places; and p-values will be presented to four decimal places.

Missing Date Procedures

Adverse events with completely missing dates will be considered treatment-emergent.

Medications with completely missing end dates will be considered concomitant. Adverse events and medications with partially missing start or end dates will be considered treatment-emergent and concomitant respectively unless the non-missing portion of the dates definitively proves otherwise.

For example, if a subject starts treatment on 20FEB2016, then adverse events with onset dates of FEB2016, 2016, or 05DEC would all be considered treatment-emergent, while onsets dates of 2015 or JAN2016 would not be considered treatment-emergent. Medications starting or ending in FEB2016 or 2016 would be considered concomitant, medications ending in JAN2016 or 2015 would not.

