6.2 Efficacy Endpoints

Primary Endpoint:

The primary efficacy endpoint is the change from baseline in alkaline phosphatase (ALP) at Week 16 in Saroglitzazar magnesium (2 mg and 4 mg) treatment.

Document Title:	Statistical Analysis Plan		
Version Number:	2.0	Date:	11 Nov 2019
Protocol Number:	SARO.16.004	Sponsor Name:	Zydus Discovery DMCC

Secondary Endpoints:

The following secondary efficacy endpoints will be evaluated in Saroglitzazar magnesium (2 mg and 4 mg) treatment as compared to placebo:

- Change from baseline in ALP at Week 4, Week 8, and Week 12 and Week 16.
- Change from baseline in lipid profile (TG, TC, HDL, LDL and VLDL) at Week 4, Week 8, Week 12 and Week 16.
- Change from baseline in liver biochemistries (GGT, ALT, AST, bilirubin and albumin) at Week 4, Week 8, Week 12 and Week 16.
- Change from baseline in serum total bile acids at Week 4, Week 8, Week 12 and Week 16.
- Change from baseline in 7 α -hydroxy-4-cholesten-3-one (C4) at Week 16
- Change from baseline in fibroblast growth factor 19 (FGF 19) at Week 16.
- Proportion of subjects with ALP improvement of 15%, 20%, 30%, 40% and normalization at Week 8 and Week 16.
- Change from baseline in QoL at Week 16 by using PBC-40.
- Safety and tolerability of Saroglitzazar magnesium 2 mg and 4 mg.
- Pharmacokinetics of Saroglitzazar.

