6.4 Statistical Methods for Efficacy Analyses

The primary efficacy endpoint, change from baseline in ALP value at Week 16 will be analyzed separately for Saroglitzazar magnesium 2 mg and 4 mg using a two-sided paired t-test. The primary analysis will be performed using MITT population with LOCF as imputation method for missing values.

The analysis for the secondary efficacy endpoints, change from baseline in ALP at Week 4, Week 8, Week 12 and week 16, change from baseline in lipid profile (TG, TC, HDL, LDL, and VLDL), liver biochemistries (GGT, ALT, AST, bilirubin and albumin), serum total bile acids, 7 α -

Document Title:	Statistical Analysis Plan		
Version Number:	2.0	Date:	11 Nov 2019
Protocol Number:	SARO.16.004	Sponsor Name:	Zydus Discovery DMCC

hydroxy-4-cholesten-3-one (C4) and fibroblast growth factor 19 (FGF 19) and change from baseline in QoL (PBC40) total scores will be analyzed using ANCOVA (Analysis of covariance) model using baseline values and treatment as factors. The p-value for the treatment comparison, estimate of LSMEANS treatment difference (Saroglitazar magnesium (2 mg and 4 mg) – Placebo), and the 95% confidence interval of the LSMEANS difference will be generated from ANCOVA model. Observed and change from baseline values will be summarized descriptively at each visit for all secondary efficacy endpoints.

Frequency and percentage of subjects with ALP improvement of 15%, 20%, 30%, 40% and normalization (achieving abnormal to normal values) at Week 8 and Week 16 will be presented. Difference between the treatment groups will be presented using 95% exact confidence Interval for proportion.

For the PBC40 questionnaire responses, descriptive summaries will be provided for the total and also for each dimensional score.

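### The stated alternative for the primary ALP test is a rise (worsening), and it matches neither the two-sided test in the SAP nor a conclusion rule with a sign

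*Protocol*

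**What the plan says.** **SAP.** Section 6.2 states: "The primary efficacy endpoint is the change from baseline in alkaline phosphatase (ALP) at Week 16" in the two saroglitazar arms. Section 6.1, which covers the efficacy analyses in general, fixes the sign: "Change from baseline = Post baseline value – Baseline value". Section 6.3 writes the primary hypotheses for 2 mg or 4 mg as H0: μ_s ≤ 0 against H1: μ_s > 0, with μ_s the change from baseline in ALP. Section 6.4 analyses each dose separately "using a two-sided paired t-test".

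**Protocol.** Section 8.2 sets H0: μ_s = 0 and "Alternative hypothesis $H_1: \mu_s > 0", with μ_s again the change from baseline in ALP. Its last sentence says that rejection shows a significant change in 2 mg and 4 mg, "hence the test drug is effective". The primary endpoint in 6.1.1 is worded as "Improvement in ALP levels after 16 weeks". Section 8.3.2.1 says "improvement from baseline to week 16 will be evaluated using Paired t-Test", with significance at p < 0.05 and no statement of sidedness. The protocol's only formula for change, "Change = (Post-baseline – Baseline", stands in 8.3.2.2 under the secondary analysis.

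**The concern.** Patients enter with ALP at or above 1.67 times the upper limit of normal (Protocol 4.2). The protocol's endpoint is improvement, and SAP 6.4 describes normalization as moving from abnormal to normal. Benefit is therefore a fall, which is a negative change under the stated formula. The written alternative points the other way.

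Three things that should agree for the primary endpoint do not:

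- The hypothesis is one-sided and points towards harm.
- The test is two-sided.
- The sentence that turns a rejection into a claim of effectiveness names no direction.

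An analyst who follows SAP 6.3 literally and one who follows SAP 6.4 would reach opposite answers on the same data. Prespecification is meant to remove exactly that choice.

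**Working it through.** The documents give no effect size, SD or power (SAP 4 says that no formal sample size estimation was done), so there is no planned figure to reproduce. The check is of sign and sidedness, with two small calculations to show size.

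**Inputs**
- 12 patients per arm (Protocol 8.5, SAP 4), so df = 12 - 1 = 11.
- Significance at p < 0.05 (Protocol 8.3.2.1).
- Two-sided paired t-test for each dose separately (SAP 6.4).
- Change = post-baseline minus baseline (SAP 6.1).
- Assumed for illustration only: mean change -20, SD of change 25, in any common unit. Only their ratio, -0.8, matters.

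**Step 1. Sign.** If ALP falls, post-baseline minus baseline is below 0.

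| Source | H0 | H1 | Where a fall lies |
|---|---|---|---|
| SAP 6.3 | μ_s ≤ 0 | μ_s > 0 | inside H0 |
| Protocol 8.2 | μ_s = 0 | μ_s > 0 | in neither hypothesis |
| Test in SAP 6.4 | μ_s = 0 | μ_s ≠ 0 | inside H1 |

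The three rows differ, and only the third has room for the result that the trial hopes to see.

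**Step 2. Hypothesis as written against test as planned.**

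t = mean / (SD / √n) = -20 / (25 / √12) = -20 / 7.217 = -2.771, df = 11.

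- Two-sided p (SAP 6.4): 0.018. The critical |t| is 2.201, so this is significant.
- Upper-tail p (H1 as written in SAP 6.3 and Protocol 8.2): 1 - 0.018/2 = 0.991.

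The mirror image, a mean change of +20, gives t = +2.771 and the same two-sided p of 0.018. The two-sided p-value carries no sign, so the direction has to come from the conclusion rule.

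**Step 3. Conclusion sentence taken by itself.** With no true change, the two-sided test at 0.05 gives a significant rise with probability 0.05 / 2 = 0.025 in each dose arm. Taking the arms as independent:
- at least one dose: 1 - 0.975² = 0.049, or 4.9%;
- both doses: 0.025² = 0.0006, or 0.06%.

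Which figure applies depends on whether the words 2 mg and 4 mg in Protocol 8.2 mean both doses together or each dose in turn. The protocol does not say. SAP 6.3 uses the word or, and SAP 6.4 tests the doses separately.

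**The case against.** **The protocol does give a direction.** Section 8.2 introduces its hypothesis as that of the primary endpoint, the endpoint is improvement, and the analysis sentence in 8.3.2.1 tests improvement. Within the protocol alone, μ_s > 0 could be read as improvement above zero, because the post-minus-baseline formula appears only under the secondary analysis. This stands in part. The firm contradiction is in the SAP, where 6.1 applies to efficacy in general and 6.2 makes that change the primary endpoint. But Protocol 8.2 itself calls μ_s the change from baseline, and nowhere in either document is it defined as a reduction.

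**A directional hypothesis reported with a two-sided 0.05 test is common and harmless.** This would be so if the sign were right: the favourable tail would carry 0.025. The sidedness mismatch is minor by itself, and the wrong sign makes it matter.

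**Nothing computed changes.** This stands. The estimate, confidence interval, p-value and power of the two-sided test do not depend on how H1 is written, and the ANCOVA comparisons with placebo are untouched.

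**Stronger readings.** A reader might infer that a true fall in ALP would be missed. The documents do not support this, because the test in SAP 6.4 is two-sided and detects a fall. A reader might also infer that the sponsor would call a rise effective. Only the last sentence of Protocol 8.2, read in isolation, permits that; the word improvement elsewhere in the protocol points the other way.

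**Conclusion.** The point holds as a defect in the prespecified primary hypothesis and conclusion rule. It is not a defect in the calculation. In the SAP the stated alternative is a rise in ALP and every fall is inside the null. Protocol 8.2 shares that alternative, although the contradiction is less explicit there. The one-sided hypothesis disagrees with the two-sided test, and the sentence that declares the drug effective has no sign of its own.

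The size is best shown by the illustration: p = 0.018 from the planned test against 0.99 for the alternative as written, on the same data. It rests on an assumed mean of -20, SD of 25 and n = 12. The 2.5% chance of a significant rise per dose assumes no true change and the usual t-test conditions. The 4.9% and 0.06% also assume independent arms, and neither should be quoted without the other. These are chances under a literal reading of one sentence, not an error rate that the trial is likely to incur.

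This should be corrected, because it concerns the primary endpoint and the stated basis for calling the drug effective. It gives no reason to doubt the planned test.

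**What to change.** Use the same text in SAP 6.3 and Protocol 8.2, for each dose separately:

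> μ_s is the mean change in ALP from baseline to Week 16 (post-baseline minus baseline) in that dose arm. H0: μ_s = 0; H1: μ_s ≠ 0; two-sided 0.05. A reduction in ALP from baseline is concluded only if p < 0.05 and the mean change is below 0.

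Replace the last sentence of Protocol 8.2 with that conclusion. The wording should stop at a reduction from baseline and should not claim benefit or effectiveness: the test is a within-arm comparison without a control, in patients selected for high ALP, and the comparison with placebo is secondary. Leave SAP 6.4 unchanged.

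The cost is a short SAP revision before database lock, which SAP 1 allows, and a protocol amendment that is documented, dated and signed as Protocol 9.5 requires, with the usual ethics committee and regulatory steps. No new data are needed, and the test and its power stay the same.
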